**Angle Labor Pain Questionnaire Turkish Version: Validity and Reliability Study and
Evaluation of Efficacy With a Non-pharmacological Method**

04 February 2021

ID: ALPQT_NONFARMA

NCT number: Not available

STUDY PROTOCOL

Study design and participants

The randomized experimental study was conducted with two parallel groups consisting of 60 pregnant women (administration group n:30; control group n:30) who met the inclusion criteria (Figure 2). The inclusion criteria of the study were similar to the first stage; in addition, pregnant women who had any contraindications for applying a back massage were excluded from the study. The sample size in the study group and control group was determined by power analysis in the PASS 11 package program. The sample calculation was made as per the pain score averages of the experimental and control groups in the study conducted by Karami et al. (2007) evaluating the effectiveness of massage practice in managing labor pain (Karami, Safarzadeh, & Fathizadeh, 2007). The calculation set forth that at least 28 pregnant women should be available for each group with a power level of 0.80 and a confidence level of 95% (Type 1 margin of error 0.05).

-Randomization and blinding

For the assignment of the participants to the groups, two separate number sequences were formed by defining the range of numbers 1—80 in the "Research Randomizer" in the computer environment, despite possible data loss. Considering their order of participation in the study, the pregnant women were assigned to the groups (study group and control) in accordance with the randomization sequence. Pregnant women assigned to the study group were also informed about the lower back massage application.

Assignment of the participants to the groups, applications, pain evaluations, and data analysis were performed by the researchers because of the nature of the study (thesis). Therefore, blinding was not performed in the study.

-Instruments and Interventions

“Pregnant Information Form,” “Labor Follow-up Form,” and “VAS” were used in the first stage, and the Turkish version of the A-LPQ. Basic information for the pregnant women was obtained from patient files. The "Pregnant Identification Form" and "Labor Follow-up Form" (Angle et al., 2017; Hamlacı & Yazıcı, 2017), which were prepared based on the literature, were used for the collection of the study data. The Visual Analog questionnaire and A-LPQ Turkish draft were used for the evaluation of the labor pain.

-Pregnant Identification Form: This form was composed of 23 questions regarding socio-demographic characteristics (age, education, occupation, social security, and family type) of the pregnant women and their obstetric history and characteristics (number of births, delivery method, complaints about current pregnancy, receiving antenatal care, etc.) (Angle et al., 2017, 2016; I. M. Gönenç & Terzioğlu, 2020; Hamlacı & Yazıcı, 2017).

-Labor Follow-Up Form: This form consisted of information about the week of pregnancy, the onset of labor and interventions performed in the first stage of labor (amniotomy, showering, oral feeding, etc.), maternal health, and the progression of labor (blood pressure, arterial pulse, body temperature, cervical dilation and effusion, condition of membranes, fetal head level, and heart rate) (Angle et al., 2017; Hamlacı & Yazıcı, 2017; Türkmen, 2017).

-Visual analog scale (VAS): VAS is a one-dimensional questionnaire used to evaluate perceived pain. VAS was first developed by Price et al. (1983) (Price et al., 1983). Cline et al. (1992) stated that the vertical use of the VAS was better understood by the patients in their study to ensure standardization in the VAS (Cline et al., 1992). VAS was used in the vertical form in the present study.

-Angle Labor Pain Questionnaire (A-LPQ): It is the first measurement tool developed by Angle et al. to measure labor pain. The original questionnaire consists of 22 items and five sub-dimensions (Angle, 2013; Angle et al., 2017, 2016). Each item in the questionnaire is scored between 0 and 10. Two of the sub-dimensions of the questionnaire are scored 0-50 and the other three sub-dimensions are scored 0-40. A total of 220 points is obtained from the questionnaire, and an increase in the total score is interpreted as an increase in labor pain with no cut-off point. ***A-LPQ was used in this study with its Turkish translation and cultural adaptation.*** Language and content validity was performed to obtain the Turkish draft version of the A-LPQ. Relevant permissions were obtained from the authors who developed the questionnaire via e-mail on 02.05.2017, and a contract was signed with Mapi Thrust, the research company holding the copyright of the questionnaire, on 22.01.2018. Turkish translation and cultural adaptation of the A-LPQ was performed in six stages (Figure 1); (1) The questionnaire was translated from English, its original language, to Turkish by an obstetrician, who was an expert in the field, and another person who was not a healthcare professional, both native Turkish speakers. (2) The Turkish draft version of the questionnaire was formed by analyzing the two different Turkish translations. (3) The Turkish draft version of the questionnaire was translated back into English by another independent translator whose native language was Turkish, who had a good command of English, and did not

know the original version of the A-LPQ. Certain language and grammar revisions were made at this stage (5). The final Turkish version of the questionnaire was evaluated for content validity by nine experts in the field, in accordance with the Davis method. Experts rated each item in accordance with the Davis method as follows: a: "Appropriate," b: "Should be slightly revised," c: "Should be substantially reviewed," and d: "Not appropriate." Intraclass correlation coefficient (ICC) analysis was performed with the data obtained from the nine experts to evaluate the consistency between the expert opinions given for each item of the A-LPQ. The "Coverage Validity Rate" was obtained for each item and the "Coverage Validity Index" was obtained for the total questionnaire, and 0.80 was taken as a reference (F. Y. Karakoç & Dönmez, 2014; Yurdugül, 2005). (6) A pre-application was made with 20 pregnant women in order to eliminate spelling, expression, and grammar problems of the Turkish version of the questionnaire, and the Turkish form was finalized.

Interventions group: The VAS and A-LPQ forms were administered to evaluate the perceived pain levels of the pregnant women before the application after they were informed about the study and their consent was obtained (First measurement). The application was initiated immediately after the pain evaluation (max. 1 min later).

Lower back massage performance: In the study, Linda Kimber's massage protocol was used (Kimber, 1999). The researcher applied the lower region circular hip massage, sacral pressure massage, and lateral lower region circular back massage to the pregnant women in the treatment group as per the Linda Kimber massage protocol (Figure 1). First, the researcher ensured that the patient was holding the bed, squatting, or bent over on the bed, which is suitable for the massage, between two contractions. The pregnant woman was instructed to breathe deeply and exhale

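### The described allocation (two number sequences over 1–80, used in order of entry, with no stated blocking, concealment, stopping or replacement rule) does not guarantee the stated 30:30 split and leaves a route to selection bias

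*Combined protocol and SAP*

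**What the plan says.** All references are to the combined protocol and SAP.

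- **Study design and participants.** There are 60 women in two parallel groups ("administration group n:30; control group n:30"). The size calculation requires that "at least 28 pregnant women should be available for each group".
- **Randomization and blinding.** For assignment, "two separate number sequences were formed by defining the range of numbers" 1 to 80 in a web randomiser, with possible data loss given as the reason for the range. Then "Considering their order of participation in the study, the pregnant women were assigned to the groups" following the sequence. The researchers did the assignment, the massage, the pain evaluations and the analysis, and there was no blinding.
- **Data analysis.** Intention-to-treat was not used.

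The text does not say how many numbers each sequence held, whether a number could appear in both, whether there was blocking, who held the list, or whether it was concealed. It also does not say whether recruitment ended at a total or at a count per arm, or what happened to the number of a woman who was lost. The flow chart is not reproduced in the text available here.

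**The concern.** An exact 30:30 split is a property of some allocation schemes, such as a list balanced at 60 or blocks that divide 60. It is not a property of a longer unblocked list read in order of entry. If the method does not produce the split, something else did: closing an arm once it was full, passing over numbers, or making up losses from the spare numbers. The plan describes none of these, but each would give the person assigning women knowledge of, or discretion over, the next assignment.

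That matters more here than in most trials. The assigner also recruits, delivers the massage and collects a self-reported pain score, without blinding. Women who are lost or do not complete can drop out of the analysis. If the last assignments can be foreseen, a woman in unusually severe or mild pain can be approached sooner, later or not at all.

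**Working it through.** **Inputs from the documents:** range 1–80; 60 women, 30 per arm; minimum 28 per arm; power 0.80; type I error 0.05. **Assumptions:** a two-sided test, and 80 numbers divided 40/40 between the two sequences without overlap.

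**1. The plan's own figure.** The minimum of 28 cannot be reproduced, because no means or standard deviation are given; the text says only that "The sample calculation was made as per the pain score averages of the experimental and control groups" in an earlier massage study. It can be inverted to an implied standardised difference:
- Normal approximation: d = (1.960 + 0.842) × √(2/28) = 0.749.
- t-test: d ≈ 0.762.

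**2. Split after the first 60 of a 40/40 list.** The number X in one arm is hypergeometric (80 numbers, 40 for that arm, 60 used).
- SD = √[60 × 0.5 × 0.5 × (80 − 60)/(80 − 1)] = √3.80 = 1.95.
- P(X = 30) = C(40,30) × C(40,30) / C(80,60) = 0.203.

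So about one list in five gives 30:30 at woman 60, and about four in five do not. With simple (coin-toss) randomisation of 60, P(30:30) = 0.103. With a list balanced at exactly 60, it is 1.

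**3. Continuing until both arms hold 30.** Simulation of 40/40 lists (100,000 lists):

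| Quantity | Mean | 95th percentile |
|---|---|---|
| Woman at whom the first arm reaches 30 | 56.2 | 59 |
| Woman at whom both arms have reached 30 | 62.4 | 66 |

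The second event falls after woman 60 in about 80% of lists (1 − 0.203). There are then two ways to finish at exactly 30:30.
- Close the full arm and send everyone else to the open one. The remaining 60 − 56.2 ≈ 4 assignments (95th percentile 9) are certain in advance.
- Keep to the list and pass over, or later remove, the surplus in the arm that filled first. That is on average 62.4 − 60 = 2.4 numbers.

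**4. If the sequences could overlap.** Two sets of 40 drawn independently from 80 share 40 × 40/80 = 20 numbers on average and leave 20 in neither, so half the positions would have no defined assignment. This reading fits poorly with the statement that women were assigned following the sequence. It does show why mutual exclusivity needs to be stated.

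**5. Power.** Two-sample t-test at d = 0.762: 0.827 at 30:30, 0.823 at 27:33, 0.820 at 26:34. Imbalance costs less than 0.01.

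**The case against.** The strongest reply is that this is a gap in reporting, not a shown failure. An unblocked list is valid randomisation. Reading it until each arm has 30 works comfortably within 80 numbers. No passage describes skipping, replacing or closing an arm. Lack of blinding and concealment is a weakness whatever the number range. Much of this stands: nothing shows that allocation was manipulated, and silence on blocking does not prove that there was none. But recruiting until 30 per arm is not stated either, and step 3 shows that it ends in foreseeable assignments or surplus numbers.

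Three stronger readings are tempting, and the documents do not support them.

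- **That only 60 women were enrolled.** The text does not say whether 60 is the number randomised, completed or analysed. A range extended for data loss and an analysis not by intention to treat both leave room for more than 60 randomised.
- **That an arm falls below 28 in about one list in five.** The figure is 0.196 under a 40/40 split with a hard stop at 60, neither of which is stated. It is 0 for balanced lists of 60, 62 or 64 or for recruiting to 30 per arm, 0.084 for a balanced list of 70, and 0.519 for simple randomisation.
- **That power drops to about 0.70–0.72.** This takes a 25% loss off the 60, leaving 22–23 per arm. The documents state no loss rate. The 20 spare numbers are 25% of 80, and 80 − 20 is already 60.

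**Conclusion.** The concern holds in a limited form. The method as written does not guarantee 30:30. Under the assumed 40/40 split, exactly 30:30 arises unaided in about 20% of lists; otherwise reaching it means about four assignments known in advance or two to three numbers passed over, on average. These sizes rest on the 40/40 assumption. The lack of a guarantee does not: it follows from the absence of any stated blocking, stopping or replacement rule.

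The consequence is possible selection bias on a subjective outcome, not loss of power. The documents show that the route is open; they do not show that anyone used it. The change should be made, since it is cheap and the unblinded, single-team conduct leaves little other protection.

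**What to change.** **For any further enrolment:**
- Use one 1:1 permuted-block list with random block sizes (for example 4 and 6), generated before enrolment. If the block sizes are chosen to sum to 60, the list gives exactly 30:30; if the last block is cut at woman 60, the worst split is 31:29.
- Hold it in sealed, numbered, opaque envelopes, each opened only after consent and the first measurement.
- Every randomised woman keeps her number. No number is skipped and no woman is replaced.

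The cost is one list and a set of envelopes. Block ends are slightly more predictable, which random block sizes limit. The plan has massage starting within a minute of the first measurement and gives the massage group extra information, so envelope opening has to be fitted into that sequence.

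**If enrolment is complete,** as the past tense suggests, the list cannot be changed. Report the numbers in each sequence, whether they were mutually exclusive, any blocking, who held the list, the stopping rule, any skipped or replaced numbers, and the numbers randomised and analysed per arm. This costs only the writing.
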